03/27/2019	11.2	Changed frequency of ECHO to D1 of every cycle
03/27/2019	14.0	Added toxicity monitoring plan

Protocol Summary

Protocol Number/Title	CASE 2918: A Phase II Study of CPX-351 as a Novel Therapeutic Approach for Patients with Myelodysplastic Syndromes (MDS) after Hypomethylating Agent Failure
Study Phase	Phase II
Brief Background/Rationale	
Epigenetic changes such as alterations in DNA methylation and histone modification play an important role in the pathophysiology of myelodysplastic syndromes (MDS). While hypomethylating agents (HMAs) such as azacitidine and decitabine have become the standard of care for patients with higher-risk MDS, they have limited efficacy. Response rates range from 20-40% and last a median of 9-10 months. Complete remissions are rare and the majority (50-70%) of patients remains resistant/refractory to these drugs. The poor success of HMAs is due, in part, to the limited understanding of mechanisms that underlie resistance. Given the poor survival of patients who fail HMAs, novel agents that overcome HMAs failure are desperately needed. Despite several novel compounds that have been investigated at the time of HMA failure, no therapy has proven to show overall survival (OS) compared to conventional care. This in part is due to the lack of our understanding into the mechanisms of resistance to HMA and the failure of accurately risk stratifying patients in this setting.
 
We have previously shown that IPSS, IPSS-R and other commonly used MDS prognostic models, (e.g., the World Health Organization (WHO) classification-based Prognostic Scoring System (WPSS), and the MD Anderson Prognostic Scoring System (MDAPSS) have limited predictive power in the HMA failure setting¹⁻⁴. We therefore developed and validated a new model to predict outcome of patients after hypomethylating agent failure (HMAF) that includes 6 clinical variables: age, performance status, complex cytogenetics (≥ 4 abnormalities), marrow blast percentage $>20\%$, platelet count, and red cell transfusion dependency⁴. This model separates patients into two risk categories: lower-risk, with a median OS of 11.0 months (95% CI 8.8-13.6); and higher-risk disease, with median OS of 4.5 months (95% CI 3.9-5.3)⁴. The model

	
was subsequently validated in an independent cohort of 223 MDS patients derived from the Groupe Francophone des Myélodysplasies (GFM) database and in a phase III randomized clinical trial. Thus, risk stratifying MDS patients by the new model at the time of HMA failure may open new opportunity for drug approvals in this setting⁵⁻⁶.
 
Identifying novel drugs that can improve the outcome of MDS patients after HMA failure remains an unmet need.

Primary Objective	
Evaluate the efficacy of CPX-351 as measured by overall response rate (ORR), i.e. by IWG 2006 criteria for MDS patients after Hypomethylating agent failure.
 
Endpoint and time frame: Overall response rate (ORR), i.e. by IWG 2006 criteria for MDS and patients at end of induction (C1D35 +/-10).

Secondary Objective(s)	
 • To determine the time to response (TTR) associated with CPX-351 in patients with MDS 
Endpoint and time frame: TTR associated with CPX-351 in patient with MDS at the end of induction (C1D35 +/-10).
 
 • To evaluate the duration of response (DOR) in patients achieving a response 
Endpoint and time frame: DOR in patients achieving a response at the time of response (C1D35 +/-10) and up to 1 year after the end of treatment.
 
 • To evaluate the event-free survival (EFS) and the overall survival (OS) probability of all patients enrolled in this trial. 
Endpoint and time frame: EFS and OS probability of all patients enrolled in this trial at end of induction (C1D35 +/-10) and up to 1 year after the end of treatment.

Estimated Study Duration	
Estimated date first subject enrolled: March, 2019
 
Estimated date last subject enrolled: March, 2020

Duration of Participation	Patient participation is expected to average 6 to 12 months
Sample Size	25 patients

Disease sites/Conditions	Myelodysplastic Syndrome (MDS)
Interventions	
 • CPX-351 44mg/m² (daunorubicin 44 mg/m² and cytarabine 100 mg/m²), IV days 1, 3, and 5 during the induction phase. • CPX-351 15.4mg/m² (daunorubicin 15.4 mg/m² and cytarabine 35 mg/m²), IV every 28 days for up to 4 cycles during the consolidation phase for patients achieving a response.

Abbreviations

AE	Adverse Event
ALL	Acute Lymphoblastic Leukemia
ALT	Alanine Aminotransferase
AML	Acute Myeloid Leukemia
AML-MRC	Acute Myeloid Leukemia with Myelodysplasia Related Changes
ANC	Absolute Neutrophil Count
AST	Aspartate Aminotransferase
AZA	Azacitidine
BSA	Body Surface Area
BUN	Blood Urea Nitrogen
CCCC	Case Comprehensive Cancer Center
CCF	Cleveland Clinic Foundation
CI	Confidence Intervals
CTCAE	Common Terminology Criteria for Adverse Events
CR	Complete remission
CRi	Complete remission with incomplete count recovery
CRF	Case Report Form
DAC	Decitabine
DCRU	Dahm's Clinical Research Unit
DLT	Dose Limiting Toxicity
DO.R	Duration of response
DSMP	Data Safety Monitoring Plan
DSTC	Data Safety and Toxicity Committee
ECOG	Eastern Cooperative Oncology Group
EFS	Event free survival
EOS	End of Study
EOT	End of Treatment
FDA	Food and Drug Administration
FU	Follow-up
GCP	Good Clinical Practice
G-CSF	Granulocyte-colony stimulating factor
GM-CSF	Granulocyte-macrophage colony-stimulating factor
GFM	Groupe Francophone des Myélodysplasies
Hgb	Hemoglobin
HI	Hematologic Improvement
HIPAA	Health Insurance Portability and Accountability Act of 1996
HMA	Hypomethylating agent
HMAF	Hypomethylating agent failure
HR	Hazard Ratio
HSCT	Hematopoietic stem cell transplant
HU	Hydrea

ICF	Informed Consent Form
ICH	International Conference on Harmonization
IEC	Institutional Ethics Committee
IRB	Institutional Review Board
IWG	International Working Group
LLN	Lower Limit of Normal
MDAPSS	MD Anderson Prognostic Scoring System
MDS	Myelodysplastic Syndrome
MPN	Myeloproliferative Neoplasm
ORR	Overall Response Rate
OS	Overall survival
PD	Progressive Disease
PI	Principle Investigator
PR	Partial remission
PRMC	Protocol Review and Monitoring Committee
SAE	Serious Adverse Event
SD	Stable Disease
SOC	Standard of Care
tAML	Therapy Related Acute Myeloid Leukemia
TLS	Tumor lysis syndrome
TTR	Time to response
UH	University Hospitals
ULN	Upper Limit of Normal
WHO	World Health Organization
WPSS	World Health Organization Classification-Based Prognosis Scoring System

TABLE OF CONTENTS

1.0 Introduction

1.1 Background of Study Disease

Epigenetic changes such as alterations in DNA methylation and histone modification play an important role in the pathophysiology of myelodysplastic syndromes (MDS). While hypomethylating agents (HMAs) such as azacitidine and decitabine have become the standard of care for patients with higher-risk MDS, they have limited efficacy. Response rates range from 20-40% and last a median of 9-10 months. Complete remissions are rare and the majority (50-70%) of patients remains resistant/refractory to these drugs. The poor success of HMAs is due, in part, to the limited understanding of mechanisms that underlie resistance. Given the poor survival of patients who fail HMAs, novel agents that overcome HMAs failure are desperately needed. Despite several novel compounds that have been investigated at the time of HMA failure, no therapy has proven to show overall survival (OS) compared to conventional care. This in part is due to the lack of our understanding into the mechanisms of resistance to HMA and the failure of accurately risk stratifying patients in this setting.

We have previously shown that IPSS, IPSS-R and other commonly used MDS prognostic models, (e.g., the World Health Organization (WHO) classification-based Prognostic Scoring System (WPSS), and the MD Anderson Prognostic Scoring System (MDAPSS) have limited predictive power in the HMA failure setting¹⁻⁴. We therefore developed and validated a new model to predict outcome of patients after hypomethylating agent failure (HMAF) that includes 6 clinical variables: age, performance status, complex cytogenetics (≥ 4 abnormalities), marrow blast percentage $>20\%$, platelet count, and red cell transfusion dependency⁴. This model separates patients into two risk categories: lower-risk, with a median OS of 11.0 months (95% CI 8.8-13.6); and higher-risk disease, with median OS of 4.5 months (95% CI 3.9-5.3)⁴. The model was subsequently validated in an independent cohort of 223 MDS patients derived from the Groupe Francophone des Myélodysplasies (GFM) database and in a phase III randomized clinical trial. Thus, risk stratifying MDS patients by the new model at the time of HMA failure may open new opportunity for drug approvals in this setting^{5,6}.

CASE 2918

Protocol Version 5.0

18 January 2021

Page 10

Identifying novel drugs that can improve the outcome of MDS after HMA failure remains an unmet need.

1.2 Name and Description of Investigational Agent CPX-351

1.2.1 Preclinical Data

CPX-351 is a liposomal formulation of a fixed combination of the antineoplastic drugs cytarabine and daunorubicin. These two drugs are present inside the liposome in a 5:1 molar ratio. The liposome membrane is composed of distearoylphosphatidylcholine, distearoylphosphatidylglycerol and cholesterol in a 7:2:1 molar ratio. These liposomes have a nominal diameter of approximately 100nm and are suspended in sucrose. Sterilization is achieved by filtration through a 0.22 μ m filter.

CPX-351 is provided as a sterile, pyrogen-free lyophilized formulation in 50 mL glass, single-use vials. Each vial contains 100mg/m² of CPX-351 where each vial contains 100 mg cytarabine and 44 mg daunorubicin base in liposomes. The lyophilized cake is reconstituted with sterile water for injection to obtain a homogeneous dispersion at 5 mg-2.2mg/mL (cytarabine-daunorubicin).

The pre-clinical pharmacology and toxicology are summarized in the Investigator's Brochure for CPX-351.

1.2.2 Clinical Data

Phase I study of CPX-351

In a phase 1 dose-escalation trial, CPX-351 induction was administered on days 1, 3, and 5 by 90-minute infusion to 48 relapsed or refractory patients with acute myeloid leukemia (AML) or high-risk myelodysplasia. Doses started at 3 mg/m² with dose doublings in single-patient cohorts until a pharmacodynamic effect (treatment-related adverse events or reduction in bone marrow cellularity or blast count) was observed, followed by 33% escalations in three patient cohorts until dose-limiting toxicity (DLT) occurred. The maximum-tolerated dose was 101 mg/m². DLTs consisted of hypertensive crisis, congestive heart failure, and prolonged cytopenias. Identified adverse events were similar with cytarabine and daunorubicin treatment. Response occurred at doses as low as 32 mg/m². Of 43 patients with AML, nine had complete response (CR) and one had CR

with incomplete platelet recovery; of patients with acute lymphoblastic leukemia (ALL), one of three had CR. Eight CRs were achieved among the 31 patients with prior cytarabine and daunorubicin treatment. CR in AML occurred in 5 of 26 patient's age \geq 60 years and in 5 of 17 patients younger than 60 years of age. Median half-life was 31.1 hours (cytarabine) and 21.9 hours (daunorubicin), with both drugs and their metabolites detectable $>$ 7 days after the last dose. The targeted 5:1 molar ratio was maintained at all dose levels for up to 24 hours⁷.

Phase II study of CPX-351

A randomized, multicenter, open-label, phase 2 trial was conducted to evaluate the efficacy and safety of CPX-351 compared with investigators' choice of first salvage treatment in adult patients with first relapse AML. The primary endpoint of the study was 1-year overall survival (OS), and Kaplan-Meier analysis did not show a significant difference between the two treatment groups (HR, 0.75; $P = 0.33$). Survival at 1-year was 36% and 27% ($P = 0.33$) for CPX-351 and salvage treatment arms, respectively. Patients were stratified at baseline according to the European Prognostic Index (EPI), and results showed that CPX-351-treated patients with the EPI-defined poor-risk strata demonstrated higher response rates (39.3% CPX-351 versus 27.6% salvage arm) and improvements in event-free survival (EFS) (HR, 0.63; $P = 0.08$) and OS (HR, 0.55; $P = 0.22$). The overall rates of grade 5 AEs were similar between the CPX-351 (23.5%) and salvage treatment arms (20.5%)⁸.

Phase III study of CPX-351

A phase 3, randomized, multicenter, open-label study evaluated the efficacy and safety of CPX-351 compared with conventional 7 + 3 (cytarabine for 7 days plus daunorubicin for 3 days) regimen in adult patients (60 to 75 years) with newly-diagnosed therapy-related Acute Myeloid Leukemia (tAML) or Acute Myeloid Leukemia with Myelodysplasia related changes (AML-MRC). The primary efficacy endpoint was overall survival (OS). The results showed OS was significantly greater in the CPX-351 group compared with the 7 + 3 group. The median OS was 9.56 months with CPX-351 and 5.95 months with 7 + 3 (Hazard Ratio [HR] 0.69; $P = 0.005$). Grade 3-5 non-hematologic

adverse events (AEs) occurring $\geq 5\%$ were similar between the two groups, except pneumonia (20% vs 15%) and bacteremia (10% vs 2%) were numerically higher in the CPX-351 compared with 7 + 3 groups, respectively. Also, median time to recovery of absolute neutrophil count (ANC) $\geq 500/\mu\text{L}$ and platelets $\geq 50,000/\mu\text{L}$ were longer in the CPX-351 group than 7 + 3 group⁹.

1.4 Rationale

Treatment options are limited for patients diagnosed with MDS at the time of HMA failure. Although the outcome remains poor, hematopoietic stem cell transplant (HSCT) may prolong survival for a subset of patients¹⁰. However, achievement of CR prior to transplant is important for improved outcomes¹⁰. Treatment with 7+3 chemotherapy regimen has been used, resulting in a response rate of approximately 30% in this patient population. Especially, in patients who progress to AML¹¹. Transplant remains an important option for these patients who can tolerate chemotherapy.

CPX-351 has shown better overall response rate and improved overall survival in patients with AML with underlying MDS changes compared to 7+3 suggesting that CPX-351 can be used in this patient population. Thus, we hypothesize that treating MDS patients, who failed or are intolerant to their initial treatment with HMA's, with CPX-351 will overcome HMA resistance and sensitize the MDS cells to this treatment.

2.0 Study Objectives

2.1 Primary Objective

- Evaluate the efficacy of CPX-351 as measured by overall response rate (ORR), i.e. by IWG 2006 criteria for MDS patients after Hypomethylating agent failure.

2.2 Secondary Objective(s)

- To determine the time to response (TTR) associated with CPX-351 in patients with MDS.
- To evaluate the duration of response (DOR)

- To evaluate the event-free survival (EFS) and the overall survival (OS) probability of all patients enrolled in this trial.

3.0 Study Design

3.1 Overview of Study Design

This is a phase II study of single agent CPX-351 administered at the standard FDA approved dose of 44 mg/m² (daunorubicin 44 mg/m² and cytarabine 100 mg/m²) intravenously on days 1, 3, 5 of the induction cycle. If patients achieve complete remission (CR), complete remission with incomplete count recovery (CRi) or partial remission (PR) (section 12.0, Table 2) they will be eligible to continue on to consolidation therapy, which will consist of CPX-351 at a dose of 15.4 mg/m² (daunorubicin 15.4 mg/m² and cytarabine 35 mg/m²) every 28 days. Patients can receive up to 4 cycles of consolidation therapy.

3.2 Number of Subjects

Approximately 25 patients will be enrolled in this trial.

3.3 Replacement of Subjects

Patients who receive any doses of CPX-351 will be not be replaced. Patient's slots will only be replaced if they are discontinued from the study prior to dosing with CPX-351. Missed doses of CPX-351 will be re-administered at the discretion of the treating physician.

3.4 Expected Duration of Treatment and Subject Participation

Enrollment to this study is estimated to occur over three years. Upon signing consent, patients will undergo screening to determine if the patient meets all inclusion and exclusion criteria, as outlined in section 4.1 and 4.2. Following screening, all eligible patients will be enrolled and begin induction therapy which will occur over a 35 day cycle and/or at count recovery with CPX-351 dosing on days 1, 3 and 5.

Patients who achieve a response (section 12.0, Table 2) may proceed with the consolidation phase of the trial with CPX-351 dosing on days 1 and 3 of every 28 days. Patients can receive up to 4 cycles of consolidation. Treatment will continue during the duration of the study unless patients exhibit evidence of treatment failure, disease progression, experience an unacceptable toxicity, or the investigator determines that discontinuation of treatment is in the best interest of the patient. Patients will be treated with CPX-351 based on a calculation determined from the patient's body surface area (BSA). BSA will be calculated before each day of dosing and will be based on the patient's height (measured at baseline) and weight (measured each visit).

4.0 Subject Selection

4.1 Inclusion Criteria

Each patient must meet all of the following inclusion criteria to be eligible for enrollment:

1. Patients must be \geq 18 years of age
2. Patients must give voluntary written consent before performance of any study related procedures not part of standard medical care
3. Diagnosis of MDS or MDS/MPN according to 2016 WHO criteria¹²
4. Primary therapy failure with either hypomethylating agents (decitabine or azacitidine) defined as:
 - Progression (according to 2006 IWG criteria)¹³ after initiation of azacitidine or decitabine treatment; or
 - Failure to achieve complete or partial response or hematological improvement (according to 2006 IWG)¹³ after at least 4-6 cycles (4-weeks cycle) of azacitidine or decitabine; or
 - Relapse after initial complete or partial response or hematological improvement (according to 2006 IWG criteria)¹³ observed after at least 4 cycles of azacitidine or decitabine.
5. Eastern Cooperative Oncology Group (ECOG) Performance Status \leq 2
6. Subjects must have normal organ and marrow function defined as:
 - If total bilirubin \leq 2x upper limit of normal (\leq 3 x ULN if considered to be due to leukemic involvement or Gilbert's syndrome) at the discretion of the treating physician following discussion with PI) Patients with a bilirubin level of >3 mg/dL will be excluded

- Calculated creatinine clearance value of $\geq 30\text{ml/min}$ AND a serum creatinine $< 1.5\text{mg/dL}$
- LVEF $\geq 50\%$

7. Female patients who:
 - Are postmenopausal for at least 1 year before the screening visit, OR
 - Are surgically sterile, OR
 - Agree to practice true abstinence from heterosexual contact or agree to use effective contraception without interruption during the study therapy and 90 days after the last dose
8. Male patients who:
 - Are surgically sterile, OR
 - Agree to practice true abstinence from heterosexual contact or agree to use effective contraception without interruption during the study therapy and 90 days after the last dose

4.2 Exclusion Criteria

The presence of any of the following will exclude a subject from study enrollment.

1. Prior treatment with CPX-351, or known hypersensitivity to CPX-351 or its components.
2. Prior treatment with intensive chemotherapy.
3. Patients with confirmed Wilson's disease will be excluded.
4. Diagnosis of acute myeloid leukemia (AML)
5. Any serious medical condition, laboratory abnormality, or psychiatric illness that, in the view of the treating physician, would place the participant at an unacceptable risk if he or she were to participate in the study or would prevent that person from giving informed consent.
6. Any active malignancy (unrelated, non-hematological malignancy) diagnosed within the past 6 months of starting the study drug (other than curatively treated carcinoma-in-situ of the cervix or non-melanoma skin cancer).
7. Patients with uncontrolled intercurrent illness including, but not limited to ongoing or active infection, symptomatic congestive heart failure, unstable angina pectoris, cardiac arrhythmia, or psychiatric illness/social situations that would limit compliance with study requirements.
8. Known history of HIV or active hepatitis B or C.
9. Active Wilsons disease
10. Major surgery within 2 weeks prior to study enrollment.

11. Pregnant or lactating females
12. Male and female patients who are fertile who do not agree to use an effective barrier methods of birth control (i.e. abstinence or 2 forms of contraception) to avoid pregnancy while receiving study treatment.

4.3 Inclusion of Women and Minorities

Men, women and members of all races and ethnic groups are eligible for this trial.

5.0 Registration

All subjects who have been consented are to be registered in the OnCore™ Database. For those subjects who are consented, but not enrolled, the reason for exclusion must be recorded.

All subjects will be registered through Cleveland Clinic and will be provided a study number by contacting the study coordinator listed on the cover page.

6.0 Treatment Plan

6.1 Treatment Regimen Overview Consent and Screening

Upon signing consent, patients will begin the screening phase. The screening period begins the day the patient signs consent and can take place over a 28 day period leading up to dosing on day 1 (D1). During the screening period patients will be assessed to determine if they meet eligibility for this study per the inclusion and exclusion criteria as outlined in sections 4.1 and 4.2. Once the patient is deemed eligible they will be stratified into two arms based on the post-HMA failure model (Appendix V).

Stratification

Prior to beginning treatment, all eligible patients will be stratified into low vs. high risk based on the post-HMA failure model (Appendix V)⁴. Seven patients will be enrolled into the low risk arm and seven patients will be enrolled into the high risk arm. Once 14 patients, across both arms, have been enrolled and evaluated for a response (D35 +/- 10 days bone marrow), an interim analysis will be conducted to determine benefit in

each arm. The arm with the greatest response will then enroll an additional 11 patients, for a total of 18 patients in that arm. Overall, this study will enroll 25 patients.

Induction

The induction phase is defined as the time between the first day (D1) of study drug to day 35 and/or count recovery. During the induction phase of the study, all patients will be treated with the FDA approved standard dose of CPX-351 at 44mg/m² (daunorubicin 44 mg/m² and cytarabine 100 mg/m²) on days 1, 3, and 5. Study drug will be administered per the study calendar (section 11.2) unless patient exhibits any EOT criteria. Premedication with anti-emetics is recommended prior to treatment with CPX-351. No re-induction will be allowed and no day 14 bone marrow biopsy is required. A bone marrow biopsy and aspirate will be obtained on day 35 +/-10 days to confirm response. If no evidence of blasts > 5%, G-CSF will be allowed to improve counts at the discretion of the treating physician. Following the bone marrow, patients who meet the response criteria per section 12.0 can then continue onto the consolidation phase of this study.

Consolidation

The consolidation phase is defined as C2D1 to C5D28 or once the patients meet EOT criteria (section 6.3, Table 1). Only patients with a documented response (CR, CRI, or PR) from the D35 (+/-10 days) bone marrow are eligible for consolidation therapy. Prior to the first cycle of consolidation therapy the patients must have a PS of 0-2. During the consolidation phase, CPX-351 must be given no earlier than 35 days after the start of induction and no later than 75 days after the start of induction. For all subsequent cycles, there must be at least 35 days between the start of each cycle. Patients must have recovered to ANC >500/ µL and platelets >50,000/µL to be eligible for any consolidation therapy.

During the consolidation phase, CPX-351 will be given at 15.4 mg/m² (daunorubicin 15.4 mg/m² and cytarabine 35 mg/m²) on days 1 and 3 of each 28 day cycle. Consolidation therapy can be continued up to 4 cycles in the absences of toxicities or reasons that require discontinuation and/or any EOT criteria (section 6.3, Table 1).

Premedication with anti-emetics is recommended prior to treatment with CPX-351. No other chemotherapy consolidation treatment is permitted. Only HSCT (hematopoietic stem cell transplant) is permitted in place of, or following, chemotherapy consolidation. Delays in administrating consolidation cycles will be allowed at the discretion of the treating physician and after discussion with the PI.

End of Treatment and Follow-up

At the point in which the patient completes therapy per protocol or meets any EOT criteria (section 6.3, Table 1), the patient will enter into the follow-up period. The patient will be followed for survival for 1 year and/or until death, whichever occurs first. During the first 6 months of follow-up the patient will be seen in clinic as standard of care (SOC) every 30 days, per the study calendar (section 11.2). End of study (EOS) is defined as the time the patient completes 1 year of follow, withdraws consent and/or patient's death, whichever occurs first.

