14.0 STATISTICAL CONSIDERATIONS

In determining the sample size for the patient cohort, Minimax Simon's two-stage design (Simon, 1989) will be used. The null hypothesis that the true response rate is 0.1 will be tested against a one sided alternative. In the first stage, 7 patients will be accrued in each arm. If there are two or less responses in these 7 patients, the arm will be stopped. Interim analysis will be conducted to determine the benefit of applying the drug in each arm. In the winning arm, 11 additional patients will be accrued for a total of 18. The null hypothesis will be rejected if 4 or more responses are observed in 18 patients. This design yields a type I error rate of 0.1 and power of 0.8 when the true response rate is 0.3.

Descriptive statistical analysis will be calculated, including histograms or box-plots, proportions, range, means and standard deviations. Fisher's exact test and Wilcoxon rank test will be used in univariate analyses of categorical and continuous variables, respectively. Overall response (CR + CRI +) rate and its 95% CI. Given there is no adjustment for multiple comparisons, need to note the p-values from the univariate analyses will be nominal and not used to infer significance.

Toxicity Monitoring Rules

The following toxicity monitoring plan will terminate the trial early given evidence for excessive rates of toxicity with CPX-351 based on the method of Thall et al.¹⁴ Early termination will be applied to evaluate patients experiencing toxicity defined as any grade ≥ 3 non-hematologic AE that is determined to be at least possibly related to CPX-351. A total of 25 patients will be enrolled. The monitoring rules target a toxicity rate of 20% and assume a non-informative Beta (0.2, 0.8) prior distribution. The trial will stop early for toxicity if $\text{Pr}(\text{Toxicity Rate} > 0.20 | \text{data}) > 0.85$, i.e. stop early if the evidence for excessive toxicity (higher than 20%) for the target population given observed data is sufficiently high (probability > 0.85). Monitoring will be carried out

from the 3rd patient. Table 5 summarizes the resultant stopping boundaries and Table 6 summarizes the trial's operating characteristics.

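### EFS and OS pool two risk strata whose 18:7 or 7:18 mix is decided by the interim result; no analysis by stratum is planned, and the ORR estimate has no stated denominator

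*Combined protocol and SAP*

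**What the plan says.** Section 6.1 (Stratification) divides eligible patients into low and high risk by the post-HMA failure model before treatment. These groups are called arms, but every patient receives the same induction regimen, so they are prognostic strata. On enrolment, Section 14 says "In the first stage, 7 patients will be accrued in each arm". After the interim, Section 6.1 says "The arm with the greatest response will then enroll an additional 11 patients, for a total of 18 patients in that arm", for 25 patients in all.

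The secondary objectives in Section 2.2 include EFS and "the overall survival (OS) probability of all patients enrolled in this trial". The Protocol Summary repeats the all-enrolled population. No section plans EFS or OS by stratum, or any weighting of the strata.

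For response, Section 14 says "The null hypothesis that the true response rate is 0.1 will be tested against a one sided alternative" and applies the rejection rule (4 or more responses) to 18 patients, that is, the expanded stratum. The estimate is described only as "Overall response (CR + CRI +) rate and its 95% CI", with no denominator. The primary objective in Section 2.1 names MDS patients after HMA failure without a stratum.

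Section 1.1 gives the model's survival by risk group: "lower-risk, with a median OS of 11.0 months (95% CI 8.8-13.6); and higher-risk disease, with median OS of 4.5 months (95% CI 3.9-5.3" months.

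**The concern.** A single-arm survival estimate can only be read against outside figures. The figures this protocol supplies are specific to risk group and differ more than twofold. The pooled EFS and OS will come from a group that is mostly low-risk or mostly high-risk according to which seven patients happened to respond better. A pooled median OS therefore matches neither benchmark, and it could look good or poor because of case mix alone. The protocol itself argues, in Section 1.1, that stratifying by this model matters after HMA failure; pooling gives up that stratification for the survival endpoints.

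Response has a smaller version of the problem. The test covers one stratum selected by the data, the objective names the whole disease setting, and nothing says whether the estimate is over 18 patients, 25, or each stratum.

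**Working it through.** **1. The plan's own design figures.** Section 14 states "This design yields a type I error rate of 0.1 and power of 0.8 when the true response rate is 0.3". Inputs: 7 patients in stage 1, 18 in total, reject at 4 or more responses. With stage 1 cut-off r (stop at r or fewer responses), the rejection probability at true rate p is the sum over x = r+1 to 7 of P(X₁ = x; 7, p) × P(X₂ ≥ 4 − x; 11, p).

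| Stage 1 cut-off | Type I error (p = 0.1) | Power (p = 0.3) |
|---|---|---|
| Stop at 2 or fewer (as printed) | 0.0185 | 0.348 |
| Stop at 0 | 0.0893 | 0.800 |

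The 7 + 11 = 18 layout reproduces the stated figures, but the printed cut-off does not. That is a separate matter. It is relevant here because the cut-off decides how often any expansion happens.

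**2. Risk mix of the pooled set, full accrual.**
- Low-risk expanded: 18/25 = 72% low-risk.
- High-risk expanded: 7/25 = 28% low-risk.

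**3. What the mix does to OS with no drug effect.** Assumption: exponential survival in each stratum, at medians 11.0 and 4.5 months from Section 1.1. With w the low-risk share,

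S(t) = w × 0.5^(t/11.0) + (1 − w) × 0.5^(t/4.5).

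By stratum at 12 months: 0.5^(12/11.0) = 0.469 and 0.5^(12/4.5) = 0.157. Pooled at 12 months:
- w = 0.72: 0.72 × 0.469 + 0.28 × 0.157 = 0.382.
- w = 0.28: 0.28 × 0.469 + 0.72 × 0.157 = 0.245 (0.2448 unrounded, so 24%).

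Solving S(t) = 0.5 gives a pooled median of 8.42 months (w = 0.72) or 5.61 months (w = 0.28). The ratio is 8.42/5.61 = 1.50.

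**4. Range over the quoted confidence limits.**

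| Stratum medians assumed (low, high) | Pooled median, low-risk expanded | Pooled median, high-risk expanded |
|---|---|---|
| 11.0, 4.5 (point estimates) | 8.4 | 5.6 |
| 8.8, 5.3 (closest) | 7.6 | 6.1 |
| 13.6, 3.9 (furthest apart) | 9.4 | 5.2 |

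**5. Fixed weights for comparison.** With a stated mix of, say, 50:50 (illustrative only), the same calculation gives a median of 6.8 months and 12-month OS of 31%, whichever stratum is expanded.

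**6. When no stratum is expanded.** Section 6.1 reads as unconditional expansion to 25. Section 14 adds "If there are two or less responses in these 7 patients, the arm will be stopped". If both arms stop, the trial ends with 7:7. The probability of 2 or fewer responses in 7 is 0.974 at a true rate of 0.10 and 0.647 at 0.30. Under the printed rule both arms stop with probability 0.974² = 0.95 if both rates are 0.10, 0.647 × 0.974 = 0.63 if one is 0.30 and the other 0.10, and 0.647² = 0.42 if both are 0.30.

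**The case against.** **ORR.** A reader might infer that ORR is also to be reported over all 25 patients. The documents do not say so. All-enrolled wording attaches only to EFS and OS, and the ORR test is on the 18 patients of the expanded stratum. What stands is the missing denominator and an objective wider than the test.

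**Population.** A reader might also infer that the pooled results belong to no defined population. That is too strong: all enrolled patients is a defined analysis set. The defect is that its risk mix depends on the interim outcome.

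**Sample.** Nor is the final sample bound to be 18:7 or 7:18. Under Section 14 as printed, 7:7 is possible and in some scenarios the likeliest result. This limits how often the imbalance arises, but the 25-patient design is the one the protocol sets out.

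**Benchmarks.** The 11.0 and 4.5 month medians come from the prognostic-model cohort. That model scores marrow blasts above 20%, whereas this trial excludes AML and requires ECOG 2 or less and LVEF of at least 50%. The gap between strata here may differ, so the survival figures are an illustration of direction and possible size, not a forecast.

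**Consequence.** EFS and OS are secondary, with no planned test or threshold, and stratum is recorded before treatment, so an analysis by stratum could be done anyway. This is fair, and it limits the severity. But the plan names the pooled analysis and no other.

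**Conclusion.** The point holds for EFS and OS. They pool two strata in proportions set by the interim result, with no analysis by stratum or fixed weighting. Under exponential survival at the quoted medians and no drug effect, pooled median OS is 8.4 or 5.6 months and 12-month OS 38% or 24%, according only to which stratum is expanded. The size depends on full accrual to 25 and on a cohort whose eligibility may differ; over the quoted confidence limits the two pooled medians lie 1.5 to 4.1 months apart (7.6 − 6.1 and 9.4 − 5.2, from unrounded values).

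For ORR, the primary test has a defined, though data-selected, population. The faults are the unstated denominator and the mismatch with the primary objective. The primary test does not fail on this account. It is a worthwhile and inexpensive correction to the secondary analyses and to the wording of the conclusion.

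**What to change.** - In the Protocol Summary and Sections 2.2 and 14, report EFS and OS, and ORR with its 95% CI, by the risk stratum assigned before treatment.
- State the ORR denominator.
- Label any pooled estimate descriptive, or weight the strata to a reference mix stated in advance.
- Word the primary conclusion as applying to the expanded stratum, with the other stratum reported as 7 patients.
- Reconcile Section 6.1 (expansion without a condition) with Section 14 (an arm can stop, so both can), and say what is reported if the trial ends at 7:7.

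No extra patients or data are needed. The cost is wider intervals, above all in the 7-patient stratum: 3 responses in 7, for example, has an exact 95% binomial (Clopper–Pearson) interval of 10% to 82%. That imprecision is real and should be shown. Reporting by stratum also leaves one limitation to note. The expanded stratum's ORR reuses the 7 patients who led to its selection. If both true rates were 0.30, with unconditional expansion and ties split at random, its expected observed ORR would be 0.337.
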